6. STUDY SUBJECTS

Inclusion Criteria:

• Premenopausal women, aged 20-48, with regular menses and no historical or biochemical secondary cause of osteoporosis; the lower age limit is to ensure epiphyses are fused, the upper to make it less likely that women will enter menopause during the study. All subjects under age 25 will be screened prior to drug administration to rule out open epiphyseal plates.

- Documented adult fractures judged to be low-trauma (trauma equivalent to a fall from a standing height or less) and/or T \leq -2.5 or Z score \leq -2.0 at the LS, FN or TH. Inclusion criteria vary slightly based on age category:
 - Premenopausal women ages 20-35 years must have at least one major osteoporotic fracture (excluding fractures of fingers, toes and face) AND low BMD defined as a T-score or Z-score ≤ -1.5 .
 - Premenopausal women above the age of 35 years should have a history of fracture AND/OR low BMD defined as Z-score < -2.0. Women above age 35 may also be enrolled on the basis on low BMD alone, without presence of prior low trauma fracture.
- Must be willing to use effective contraception throughout the period of study drug administration

Exclusion Criteria:

- History of any condition that increases the risk of osteosarcoma (Paget's disease, skeletal irradiation)
- Early follicular phase serum FSH>20 mIU/ml (to exclude perimenopausal women)
- Disorders of mineral metabolism: 1°/2° hyperparathyroidism, osteomalacia, osteogenesis imperfecta (OI) or Ehlers Danlos (ED). Subjects will not routinely undergo genetic testing for OI or ED as part of their screening evaluation. However, each subject will have a detailed medical and family history and a complete physical examination by one of the physician investigators. Women with historical features or physical examination findings suggestive of OI or ED will be referred for genetic evaluation. If the genetic evaluation is positive for OI or ED, the subject will be excluded from participation.
- Suspicion of osteomalacia (elevated alk phos, worsening bone pain with weight bearing, or bone tenderness)
- Vitamin D deficiency (serum 25-OHD[<]20 ng/ml). Women with levels of 10-20 ng/ml will be eligible after treatment with vitamin D has resulted in levels ≥20 ng/ml.
- Pregnancy within the last 3 months if there was no lactation or lactation within past 6 months
- Prolonged amenorrhea (≥ 6 months) during reproductive years (except pregnancy or lactation)
- Prior eating disorder (hypothalamic or exercise induced amenorrhea now resolved may be acceptable if symptoms occurred at age >20 years, for <1year, >5 years ago)
- Malignancy, except cured basal or squamous cell skin carcinoma
- Endocrinopathy: new onset untreated hyperthyroidism, hypothyroidism, Cushing's syndrome, prolactinoma
- Renal insufficiency (serum creatinine above upper limit of female normal range)
- Liver disease (AST, ALT, bilirubin, total alkaline phosphatase activity above upper normal limit)
- Intestinal disorders (celiac disease, pancreatic insufficiency, inflammatory bowel disease) IBD: only Crohn's Disease or Ulcerative Colitis are exclusions
- History/current GCs, anticonvulsants, anticoagulants, methotrexate, depot progesterone, GnRH agonists
- Oral glucocorticoid use (subject will not be excluded if used dose equivalent to less than prednisone 5 mg for <3 months). Inhaled steroid exposure will require assessment of dose used.
- Current anticoagulant use (past use of warfarin (Coumadin) or low molecular weight heparin is not an exclusion)
- Depo Provera use (subjects will not be excluded if used at age>20, >5 years ago)
- Drugs for osteoporosis (raloxifene, bisphosphonates, denosumab, calcitonin, TPTD). Subjects who discontinue these medications will be eligible 3 months after stopping raloxifene or calcitonin, 12 months after stopping alendronate, risedronate, ibandronate, or pamidronate and 18 months after stopping denosumab. Subjects with prior use of zoledronate may be eligible if received only one dose >4 years ago. Total bisphosphonate exposure must be ≤ 1 year. Subjects who have taken TPTD in the past will not be eligible unless used for <3 months, > 2 years ago.

7. RECRUITMENT

Subjects from CUMC will be recruited from previously enrolled and newly recruited subjects. Recruitment to studies of uncommon diseases is always challenging. Although recruitment of cases to the original R01 grant (AAAA9245) was slow for the first 2 years, we ultimately enrolled 64 subjects with IOP. In addition, we were able to recruit 22 women to the pilot study of TPTD in Premenopausal Women with IOP in 12 months. Our study teams have developed ongoing relationships with these patients that will be useful in recruitment. We anticipate that some of the subjects in protocol AAAF2251 will come directly from protocol AAAA9245, as, in our experience, many women with IOP are anxious to pursue treatment options for their condition.

We recruit subjects locally, nationally and internationally. Locally, we recruit patients referred to the Metabolic Bone Disease Unit at CUMC in New York. We post flyers and speak at inter-departmental and inter-institutional conferences, particularly to Orthopedics and Obstetrics & Gynecology departments. We speak at national and international conferences (ISCD, NOF, ECTS, ASBMR, TES). [name] recently conducted the first ASBMR Webinar on premenopausal osteoporosis, which was attended by >200 individuals. We send biannual email reminders to physicians from surrounding states of both centers who care for patients with osteoporosis and also to our clinical colleagues in ASBMR. The study will be posted on CUMC, NOF, NIH, and clinicaltrials.gov. A large source of referrals is patients themselves.

When a patient is referred to our center, we will conduct a brief phone screening to ascertain whether the subject may be appropriate for the study. Prior to enrollment, a study investigator or research coordinator will review the study at length with the subject during the informed consent process.

8. INFORMED CONSENT PROCESS

Written consent will always be obtained according to appropriate Informed Consent forms that will be reviewed and approved by the institutional review board of the Columbia University Medical Center. Potential participants are assured that participation is voluntary and that refusal to participate will not influence their care. Statements to this effect will be included in all Informed Consent forms, which will be signed by the investigator or coordinator obtaining consent and by the subject. All investigators and coordinators have completed courses in Good Clinical Practices and HIPAA compliance. Written informed consent will be obtained for every subject by the investigators after an explanation of the purpose, risks and benefits of the study. Confidentiality will be guarded with the use of computers that are password protected and storing questionnaires with sensitive information within a locked file. All subjects will be provided with instructions on how to contact the investigative team if any problems or concerns arise.

The informed consent process will be conducted by a study investigator or research coordinator prior to initiation of study-related procedures. Subjects will have an opportunity to asked questions prior to signing the form, and all participants will receive a copy of the signed consent form for their records.

9. CONFIDENTIALITY

Confidentiality of patient data in this project will be ensured. Personal Identifying Health Information (PHI) of participants will be kept only in secure files accessible to the PI, investigators and project coordinators. Data will be recorded on case report forms on which the only identifier is a research ID code. Only the PI and project coordinator have access to the link between the research ID code and PHI. No names or identifying information will be included in research reports. Subjects' names will not appear on questionnaires. All computers housing research data have passwords and timed screen savers requiring a password for access. Through these safeguards, the confidentiality of the data will be ensured.

Information obtained in the setting in this study may be made available to the following entities:

- The investigator, study staff and other health professionals who may be evaluating the study

- Columbia University
- New York Presbyterian Hospital

- Authorized representatives of the Food and Drug Administration ('FDA'), the Office of Human Research Protections ('OHRP') or other government regulatory agencies

- Applicable Institutional Review Boards ('IRBs') that independently review the study to assure adequate protection of research participants, as required by federal regulations.

The investigator, regulatory authorities, IRB and study sponsor may keep the research records indefinitely. If the results of the study are published or presented at a medical or scientific meeting, subjects will not be identified.

10. PRIVACY PROTECTIONS

We will take all necessary steps to safeguard each participant's expectation that the information they offer will be held in confidence. These protections will apply to all research related data collection and procedures, as well as to all forums

Only a select group of study personnel will have access to patient study files. We are fully committed to safeguarding an individual's expectation that the information they offer will be held in confidence. All subjects will sign a HIPAA form in addition to the informed consent document to prevent inappropriate use or any disclosure of individuals' health information and to require any organizations which use health information to protect that information and the systems which store, transmit, and process it. The subject has the right to revoke the authorization for us to access her health information at any time, as is stated in the HIPAA form that each subject will sign prior to participation.

Our safety reporting responsibilities require the investigator to report any adverse events to the IRB, the FDA and Eli Lilly, who is providing us with the study drug. These reports will include only a study ID, and will not divulge the participant's identity.

11. POTENTIAL RISKS

The risks of this study are related to the venipuncture, radiation exposure and the study medication, teriparatide.

1) Teriparatide

a. Teratogenicity: In contrast to bisphosphonates, TPTD does not accumulate in the skeleton. Therefore, teratogenic effects, if any, would essentially be limited to the period of administration. Thus, it is a more attractive choice for treating osteoporosis in women of childbearing age, as there would be no potential for subsequent pregnancies to be affected by residual drug. All participants will be required to use effective contraception during the study.

b. Osteosarcoma: Rats exposed to TPTD, in amounts 3-58 fold higher than the human dose for the equivalent of 75 human years (18-24 rat months), develop osteosarcoma in a dose related manner. Therefore, the FDA approved TPTD for therapy of osteoporosis with a "black box" warning and recommended a 2-year limit on duration of treatment. It is highly likely that this toxicity as particular to the rat. There are marked differences in skeletal physiology between rodents and primates. The rat skeleton grows throughout most of their lives⁵⁶ and shows very little evidence for remodeling. In contrast, humans typically cease longitudinal growth by 15-20 years of age⁵⁷ and the adult human skeleton is characterized by remodeling rather than growth. Perhaps because of these differences, the anabolic response of the rat skeleton to daily PTH treatment is far greater in rats⁵⁸ than in humans⁵⁹. Most recently, in a second toxicity study in rats, a "no effect" dose was defined that was larger than any human being will experience⁶⁰. Finally, there was no evidence of any carcinogenic toxicity when the non-human

primate macaque was treated with the same toxicity $protocol^{61}$. To date, two cases of osteosarcoma have been reported in among almost 430,000 patients treated with TPTD⁶²⁻⁶⁴; this is approximately the same incidence as the 1.7 patients expected to develop osteosarcoma by chance alone, given an expected incidence of 4-5 per million. An additional case recently reported in abstract form, had osteosarcoma before TPTD was initiated⁶⁵. Moreover, the pathology of the first case was controversial and the second case developed in a man who had received pelvic radiation for prostate cancer and the cancer developed within the field of radiation, rather than in the long bones, as is typical of sporadic osteosarcoma⁶⁴. Among the millions of individuals with hyperparathyroidism who are exposed to chronically elevated levels of PTH, there are only rare reports of osteosarcoma, most of which have not been welldocumented⁶⁶. There were no reports of osteogenic sarcoma among the participants in any of the clinical trials with PTH, amounting to over 2500 patients. In the largest clinical trial with 1637 subjects, there was no increase in cancer incidence between subjects receiving TPTD and placebo and no woman developed an osteosarcoma²⁸. Given all these considerations, it appears that, in general, PTH is safe in humans and that TPTD will be a safe treatment for premenopausal women with IOP. Nevertheless, it is important that subjects in this study are informed of the rat toxicity data and the case reports. Consistent with FDA guidelines, no patient will receive active drug for more than 2 years. In addition, the dynamic histomorphometry measurements we will have will offer an extra measure of safety parameters. We plan to minimize the already small risk by excluding adolescents who may not have fused epiphyses and women with a history of skeletal radiation.

c. Hypercalcemia, Hyperuricemia and Hypercalciuria: Hypercalcemia and mild increases in serum uric acid are known side effects of PTH, although not very common at the FDA-approved 20 mcg/day dose that we will use. A post-hoc analysis of two prospective randomized clinical trials involving 1,637 postmenopausal women and 2,437 men found that urinary calcium excretion increases by an average of 32 mg/d on the 20 mcg dose of TPTD⁶⁷. [name], the Study Monitor, will monitor pre-dose serum calcium and uric acid and urinary calcium excretion at 1 to 6-month intervals to determine the incidence of these abnormalities in our study participants. We will exclude subjects with hypercalcemia (fasting serum calcium >10.2 mg/dl) and hypercalciuria (>300 mg/g creatinine) at baseline.

For subjects in the placebo group during months 0-6, there may be a risk of bone loss. However, Peris et al. reported a retrospective analysis of 16 women with IOP, managed with calcium, vitamin D and increased physical activity⁶⁸ They documented small increases in BMD and no fractures over an average 3 years of observation, supporting the safety of a placebo-controlled design. We have longitudinal BMD data in 18 women with IOP followed on calcium (1000-1500 mg/day) and vitamin D (800-1000 IU/day) for an average of 4 years. LS BMD increased by $0.8 \pm 2.9\%$, while there were slight decreases at the FN (-1.2 ± 5.3%), TH (-0.5 ± 3.4%) and 1/3 Radius (-2.4 ± 2.8%). None of the decreases were statistically significant. Thus, we do not expect major declines in BMD in the women randomized to placebo for the first 6 months and in any case, all subjects will receive teriparatide after the first 6 months.

2) Radiation

Radiation exposure (effective dose) for DXA of the spine, hip and forearm with the Hologic QDR4500 is 7.45 μ Sv, for VFA 5.2 μ Svand for Body Composition is 5.2 μ Sv. This is about the amount the average person receives from background radiation in 19 days. For HRpQCT of the forearm and leg, the estimated effective whole body dose is below 5 μ Sv per scan, since only a very small fraction of the distal forearm or leg is irradiated. Radiation exposure from a central QCT scan of the spine and additional slice for body composition is about475 μ Sv, which is equivalent to approximately 3 months of background radiation. In subjects where VFA diagnosis of fractures is ambiguous, subjects will be asked to have lateral thoracic and lumbar spine radiographs to assess presence of a vertebral compression fracture. This amounts to the equivalent of an extra 12 months of background radiation. We anticipate that the need for this additional procedure will be necessary in less than 10% of subjects.

For purposes of comparison, this amount of radiation exposure is similar to that associated with many other x-ray procedures: 45 mrem for a mammogram, 1300-1800 mrem for a standard abdominal/pelvic or chest CT scan, 6 mrem for a round-trip transcontinental plane flight and 240-360 mrem natural background radiation in a year. Expressed as equivalencies to background radiation, a standard mammogram, often obtained annually, is associated with radiation exposure equivalent to approximately 2 to 3 months of natural background radiation. A standard abdominal or chest CT scan is associated with radiation exposure equivalent to approximately 24 to 60 months of natural background radiation. Thus, the maximum amount of radiation that would be received by participation in this study (<600 mrem) is less than that from a standard CT scan of the chest or abdomen. We will counsel all study subjects about the total amount of radiation that they will receive as a result of participation as part of Informed Consent procedures of that particular study. In addition, they will be considered carefully.

Incidental findings: Upon finding of an incidental finding (IF), the clinical readers have been instructed to inform the research team of the study regarding the subject. The subject will be informed of the IF in accordance with timing related to the Class A or Class B severity by the PI of the study. Imaging results will be sent to subject's primary care provider as requested.

3) Venipuncture

The risks of venipuncture for blood drawing include pain, bleeding, bruising, and a remote possibility of infection or inflammation at the site. Additionally, there is a possible risk of syncope in individuals who are prone to vasovagal responses. To minimize these risks, trained phlebotomists who follow proper technique perform all venipunctures.

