randomized, double blind, placebo-controlled, single switch-over trial of TPTD in premenopausal women with IOP. Forty-one subjects will be assigned to TPTD (Group A; n=28) or placebo (Group B; n=13). At the 6 month timepoint, all subjects will receive TPTD, but blinding of original group assignment will be maintained for an additional 6 months. At the 12 month visit, the blind will be broken and those initially randomized to TPTD (Group A) will continue on study drug for an additional 12 months while those initially randomized to placebo (Group B) will continue for an additional 18 months, so that subjects in both groups complete 24 months of treatment overall. aBMD by DXA and HRpQCT will be measured at baseline and at 6 month intervals. vBMD by cQCT will be performed before randomization and after 24 months of TPTD (Table 1). A quadruple labeled transiliac crest bone biopsy will be performed at 3 months for both Group A and B. Eli Lilly & Company will provide TPTD and placebo but will supply no other funding. After 24 months of treatment in either Group A or B, all women will be offered three choices for follow up: the subjects can A) continue to to be followed for 12 months off TPTD B) choice to leave the study and be treated clinically using an anti-resorptive medication to maintain gains in bone density after treatment with TPTD, or C) join a new study to maintain gains in bone density after treatment. The new study is currently in the design phase and funding phase and precise details are not yet available.

Statistical Analysis Plan

2.A. Statistical Analysis Plan Our aims in this protocol are as follows:

Aim 1: To establish the efficacy and safety of 6 months of TPTD versus placebo in premenopausal women with IOP

Aim 2: To determine the effect of 3 months of TPTD on bone remodeling at the tissue level and the extent to which baseline and 3 month bone remodeling predicts response to TPTD in premenopausal women with IOP.

Aim 3: To determine the extent to which 12 and 24 months of TPTD improves areal and volumetric BMD, bone microarchitecture and strength (stiffness) compared to baseline measures in premenopausal women with IOP

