negative pregnancy test, all will have BMD, VFA and body composition by DXA. Women who fulfill BMD or fracture eligibility criteria will complete a Historical Questionnaire (Appendix 1) on medical and reproductive history (menstrual history, menarchal age, parity, OCP use), risk factors for osteoporosis (eating disorders, alcohol, tobacco, caffeine intake), personal and family history of fractures, current and past medications. The Eating Disorder Examination - Questionnaire (EDE-Q; Appendix 2) will be given to identify women with subclinical eating disorders^{45,46}. All will have a standardized physical (weight, height by Harpenden stadiometer) by a physician co-investigator and a Secondary Osteoporosis Evaluations (SOPEval). The following must be normal: blood count, Westergren ESR, C-reactive protein, electrolytes, creatinine, thyroid and liver function tests, uric acid, calcium, phosphate, 25-OHD (>20 ng/dl; those with levels between 21-29 ng/ml will be offered supplementation to achieve levels >30), intact PTH (<65 pg/ml), tissue transglutaminase IgA antibody (tTG; 99% specific and 95% sensitive for celiac disease) and immunoglobulin A (IgA) to exclude celiac disease, 24-h urine for creatinine, calcium (<300mg/gCr) (100-250 mg), free cortisol. Other tests may be performed if less common etiologies are suspected. In some cases, arrangements may be made for some portions of the screening visit procedures (eg laboratory studies) to take place outside of this medical center. In all cases, eligibility will be verified by study physicians.

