Subjects will be provided with calcium (citrate) caplets (Citracal + D; each 315 mg + 250 IU D) and a multivitamin (Centrum) that provides 500 IU of vitamin D daily. Most subjects will be instructed to take 2 Citracal caplets and a multivitamin; the total daily dose of calcium from supplements will be approximately 630 mg and of vitamin D 1000 IU. Subjects with very low dietary calcium intake (<500 mg/d estimated by interview and the FFQ), will be asked to take 3 Citracal caplets, while those with high dietary calcium intakes (>1,000 mg/day) will be asked to take 1 Citracal caplet.

Visits 4-5, 8-13 (Study Evaluations): At each study visit, study coordinators will assess any adverse events that transpired since the last study visit. Patients will be instructed to bring their Forteo journal and pens with them to every visit, which documents their compliance with the study medication. The purpose

of the 1-week and 1-month visits (Visits 4 & 5) is to monitor for compliance and adverse effects. At the 1-week and 1-month visit, we will also obtain fasting serum for serum calcium (safety) and at the 1-Month we will also collect serum for BTMs. These visits may be conducted on site for women who reside close to the study sites or may be a telephone contact and local blood draw for those who live at a distance. The remainder of the study visits to perform imaging studies and/or blood draws and dispense study drug are shown in Tables 1-3. We will perform a single follow-up cQCT scan after 24 months of TPTD treatment to minimize radiation exposure in these women who are of child-bearing age. At Visit 12, subjects will be presented with three options for post-TPTD follow up as described in the study design.

Visit 6 (Pre-Biopsy Clearance and Labeling): Subjects will have a pre-biopsy clearance visit with the surgeon and have safety bloods drawn and processed as per hospital regulations. Subjects will receive their second antibiotic labeling agent, demeclocycline, and accompanying labeling schedule.

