MD Visit		X	V	X	X				
Dispense TPTD		X	X X	X					
Telephone Contact [#]	X	X	X X	X	X				
Pregnancy Test BMD by DXA		X	X X	X	X				
History & Physical		X	Λ	X	X				
Adverse Events	v	X	Х	X	X				
Serum FSH	X	X	Λ	X	X				
HR-pQCT		x		X	X				
Central QCT		Λ		X X	Λ				
VFA by DXA		x		X	x				
		X	X	X	X				
Calciotropic Hormones		X		X	X				
Bone Turnover Markers		X	Х	X	X				
* Only for treatment									
treatment (Group A # Will occur before		luled visi	t						

Table 3: Study Visits – Group B**	9 9M	9 12M	10 18	11 24	12 30	13 42
Group D	>	12111	M	M	M	M
MD Visit		х		Х		Х
Dispense TPTD		Х	Х	Х		
Telephone Contact [#]	Х	X	Х	Х	Х	Х
Pregnancy Test		х	х	х	Х	Х
BMD by DXA		х	Х	Х	Х	Х
History & Physical		х		Х		Х
Adverse Events	х	х	Х	Х	Х	Х
Serum FSH					Х	
HR-pQCT			х		Х	Х
Central QCT					Х	
VFA by DXA		х		х		Х
Blood/Serum Archive	х	х	х	х	Х	Х
Calciotropic Hormones		х		Х		Х
Bone Turnover		х	Х	Х	Х	Х
Markers						
** Only for treatment group that started with 6 months of						
placebo injections (Group B)						

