7. Spine Radiographs: Lateral thoracic and lumbar spine radiographs for diagnosis of prevalent or incident vertebral fractures, performed using the protocol used in the Study of Osteoporotic Fractures (SOF) ⁵⁵, will be used in subjects for whom VFA diagnosis of fractures is ambiguous. Total critical organ absorbed dose from a lateral thoracic and lumbar spine radiograph is equivalent to about 350 mrem. Our skeletal radiologist, [name]., evaluates and reads these x-rays.

8. Biochemical Assays: All blood samples will be collected fasting in the morning. General tests (CBC, serum calcium, phosphate, albumin, renal and liver function tests, urine calcium and creatinine) will be run when collected by standard methods. Serum for PTH, 25-OHD, 1,25(OH)₂D, osteocalcin, BAP, P1NP, CTx, IGF-I, IGFBPs, leptin, adiponectin, insulin, glucose, IL-6, homocysteine, c-reactive protein (CRP), lipid studies, E2, testosterone, SHBG, OPG, RANKL will be aliquoted, frozen immediately and stored at -80°. Specimens will be shipped frozen from the CORC to Columbia. Additional serum/urine will be archived for measurement of BTMs and mineral metabolites that may become available in future. Blood for DNA will be obtained from peripheral blood lymphocytes for archival purposes. We intend to isolate and store these samples for future genetic studies that may identify a polymorphism linked to one of our phenotypes, or identify a new candidate gene polymorphism in our study population. Blood for osteoblasts, which are bone-building stem cells, found in the bloodstream, will be collected. These will be processed and stored frozen at -80°C. All assays are currently in place either in the CUMC Bone Marker Laboratory within the Division of Endocrinology, under the direction of [name]., PharmD or

the Core Laboratory of the Irving Institute for Clinical and Translational Research (CUMC CTSA). Lipid particle size analysis will be conducted at Liposcience, Inc.

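### Section 11 commits to repeated urine calcium monitoring, but the visit tables schedule no urine calcium test for Group B (n=13) during its 24 months on teriparatide

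*Combined protocol and SAP*

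**What the plan says.** - **The commitment.** Section 11, item 1c (hypercalcemia, hyperuricemia and hypercalciuria) says that the study monitor "will monitor pre-dose serum calcium and uric acid and urinary calcium excretion at 1 to 6-month intervals". The stated purpose is to measure incidence among participants. No end date is given, and neither group is excepted. The same item reports a mean rise in urinary calcium of 32 mg/day on the 20 mcg dose.
- **When Group B is on drug.** Section 2 assigns 28 women to Group A (teriparatide first) and 13 to Group B (placebo first). "At the 6 month timepoint, all subjects will receive TPTD", and after the month 12 visit "those initially randomized to placebo (Group B) will continue for an additional 18 months".
- **Where the schedule is set.** Section 3.A, under Visits 4-5 and 8-13: "The remainder of the study visits to perform imaging studies and/or blood draws and dispense study drug are shown in Tables 1-3".
- **The tables.** Table 1 (both groups, screening to month 6) has a row for 24-hour urine calcium/creatinine, marked at screening, 1M and 6M. Table 3 covers Group B at 9M, 12M, 18M, 24M, 30M and 42M; its footnote begins "Only for treatment group that started with 6 months of" and goes on to name placebo injections.
- **The assay text.** Section 3.B, item 8, lists general tests, among them "urine calcium and creatinine) will be run when collected by standard methods". It gives no collection times.
- **The outcome.** In section 2.A, Aim 1, the primary safety event is hypercalcemia or hypercalciuria in the first 6 months of assigned treatment.

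**The concern.** Section 1 names safety alongside efficacy as the major objective, and hypercalciuria is half of the primary safety event. The plan itself reports that the drug raises urinary calcium. Yet the only dated urine calcium tests for Group B come before these women have taken any teriparatide, so they cannot show a drug effect.

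Staff who follow the visit tables as written would not look for hypercalciuria on drug in 13 of the 41 women. Two things are at stake: the safety of those women, and the on-drug incidence that section 11 sets out to measure. A within-woman comparison is also lost, since each Group B woman already contributes off-drug values against which later ones could be set.

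**Working it through.** This is a count from the schedule. The plan gives no figure of its own to reproduce.

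**Step 1. Group B's time on drug.** Start: month 6. End: month 12 + 18 = month 30. Duration: 30 − 6 = 24 months.

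**Step 2. Reading Table 1.** The urine row has three marks. Lined up against the neighbouring bone turnover marker and blood/serum archive rows, they fall at screening, 1M and 6M.

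**Step 3. Reading Table 3.** It has 14 rows, all labelled: MD visit, dispensing, telephone contact, pregnancy test, DXA, history and physical, adverse events, FSH, HR-pQCT, central QCT, VFA, blood/serum archive, calciotropic hormones, and bone turnover markers. None is urine calcium.

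**Step 4. Setting the two side by side for Group B.**

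| Time | Group B treatment | Urine calcium scheduled |
|---|---|---|
| Screening | none | yes (Table 1) |
| 1M | placebo | yes (Table 1) |
| 6M | end of placebo, switch | yes (Table 1) |
| 9M, 12M, 18M, 24M, 30M | teriparatide | none (Table 3) |
| 42M | 12 months after treatment ends | none (Table 3) |

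The 6M test is taken as a pre-drug value, because active drug starts at that visit.

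**Step 5. Counts.**
- Off drug: 13 × 3 = 39. On drug: 0.
- Expected on drug at the longest interval in section 11: 24 / 6 = 4 per woman, and 13 × 4 = 52 if all complete treatment.
- If the 10% drop-out assumed in section 2.B all occurred before 12M: 52 × 0.9 = 46.8, about 47.
- Group B's share of planned teriparatide exposure: (13 × 24) / (41 × 24) = 312 / 984 = 31.7%.

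**Step 6. Other places where urine is mentioned.** Visit 3 (section 3.A) stores serum and urine frozen for batch assays, and section 3.B, item 8, archives further serum and urine for turnover markers and mineral metabolites. Neither is monitoring of urinary calcium. Table 1 lists the archive and the 24-hour urine test as separate rows with different marks, so the plan treats them as different procedures. No visible text dates a urine calcium test after month 6.

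**The case against.** **The commitment may cover only months 0 to 6.** Section 11 gives no duration, Table 1's post-baseline tests fall at 1M and 6M, and the only defined hypercalciuria outcome stops at 6 months. On that reading the wording is met. This stands as a point about wording, but Group B's on-drug count is still 0.

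**If the commitment runs throughout, it already obliges monitoring of Group B.** This stands too. Section 17 also mentions an operations manual that is not available here. A reader might infer that no urine would be collected from Group B on drug; the documents do not show that. They show a commitment with no scheduled visit to carry it out.

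**The tables are damaged.** Table 2 has lost a row label and Table 1's footnotes are fragmentary. That does not explain the gap in Table 3, where every row is labelled. It does limit what can be said about Group A. A reader might infer the same gap there after month 6, but the unlabelled row in Table 2 cannot be identified with certainty, although it sits where Table 3 has the archive row. No count is claimed for Group A.

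**Serum calcium and uric acid.** A reader might extend the point to these. Serum calcium has dated checks at 1 week and 1 month, and uric acid is named at screening ("thyroid and liver function tests, uric acid, calcium, phosphate"); later times are not itemised. But blood is drawn at every Table 3 visit, the general tests may be run on it, and the pharmacokinetic sub-study samples calcium on drug in six women. A gap is not shown.

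**Other safeguards exist.** Adverse events are recorded at every Table 3 visit, the DSMB meets twice a year, and Group A has on-drug urine tests at 1M and 6M. These reduce the consequence. They do not replace a urine test, because raised urinary calcium is a laboratory finding.

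**Conclusion.** The point holds for Group B and should be fixed. As scheduled, 13 of 41 women have three urine calcium tests each off drug and none in 24 months on teriparatide, against 52 at the longest interval named in section 11 (about 47 with early drop-out of 10%). This rests on the visible Table 3 being complete in its rows, on the 6M test preceding the first active dose, and, for the 52, on section 11 applying for the whole treatment period.

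Three stronger inferences are not supported:

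- **Main results.** The primary safety comparison covers the first 6 months, when both groups have the same urine tests, so it is unaffected. So is primary efficacy.
- **Unmonitored exposure.** The 31.7% is Group B's share of planned drug exposure. It is not the unmonitored share for the trial, because Group A after month 6 is unresolved.
- **Blinding.** A 12M urine test in Group A is not needed to protect the blind. The blind is broken at that visit, and the extracted tables already differ there for HR-pQCT.

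**What to change.** - **Table 3:** add 24-hour urine calcium/creatinine at the existing 12M, 18M, 24M and 30M visits, which are 6, 12, 18 and 24 months on teriparatide.
- **Table 2:** check against the source document that Group A has the same test after month 6 (12M, 18M, 24M), and add it if not.
- **Section 11:** state how long the monitoring runs. If only months 0 to 6 were meant, saying so would settle the wording but would leave Group B untested on drug.
- **Serum calcium and uric acid:** confirm that they are run on blood already drawn at the later visits. Nothing more is needed on the present evidence.
- **Analysis:** leave the primary safety analysis as it is. Report on-teriparatide hypercalciuria descriptively by time since first active dose. In Group B, the 1M and 6M placebo values are the better comparators, since the screening value is subject to the 300 mg/g creatinine eligibility limit and precedes the study calcium supplements.

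**Cost:** an amendment to the visit tables with no new visits. Group B needs at most 52 collections. Group A needs none if Table 2 already has the test, and otherwise 28 × 3 = 84. The burden is up to four extra 24-hour urine collections per woman.
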